This innovative paradigm will lay the groundwork for future studies that can directly interrogate ACh function in the living human brain. This is critical to the advancement of our understanding of ACh involvement in psychiatric and medical disorders.

Additionally, a substantial literature body demonstrates that nAChRs and the cholinergic system dynamically control the mesolimbic DA system by enhancing, inhibiting, and filtering striatal DA release. We have preliminary data suggesting tobacco smokers at 2 weeks of abstinence have blunted DA release compared to nonsmokers. We propose in Aim 7 to determine 1)

whether there is reduced DA release in smokers at 2 weeks of withdrawal vs. nonsmokers, 2) if the magnitude of DA release is correlated with alterations in ACh levels measured in Aim 4 and 3) if alterations in DA and ACh predict relapse vulnerability.

**Aim 1: To determine the test-retest reproducibility of NCFHEB binding parameters in 10 nonsmoking subjects.**  $\beta_2$ -nAChRs will be quantified twice in nonsmoking subjects. Based on preclinical evidence, we hypothesize within 20% difference of binding parameters between test and retest scans.

**CLOSED Aim 2: To determine if  $\beta_2$ -nAChR availability is genetically predisposed in never smokers and smokers** We propose to determine if the ANKK1 genotype (rs4938015/hCV38879) or CHRNA4 genotype determines  $\beta_2$ -nAChR availability in adult never smokers. Specifically, 10 never smokers and 10 smokers at one week of abstinence will be imaged using NCFHEB PET and blood samples for DNA extraction will be collected from all subjects.

**Hypothesis:** Homozygotes (TT) will have higher  $\beta_2$ -nAChR availability compared to age-, and sex matched heterozygotes that carry the C allele in the ANKK1 gene (rs4938015/ hCV38879).

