### 3.1 Overall plan:

**Aim 1: To evaluate the test-retest reproducibility of NCFHEB binding parameters in 10 healthy subjects.**

**CLOSED Aim 2: To determine if  $\beta_2$ -nAChR availability is genetically predisposed in 10 never smokers and 10 smokers at one week of abstinence with NCFHEB.**

**CLOSED Aim 3: To determine if the adaptive increase in  $\beta_2$ -nAChR availability and change in  $\beta_2$ -nAChR availability over the first month of abstinence in smokers is genetically predisposed (the same 10 smokers from Aim 2) with NCFHEB.**

**Aim 4: To measure the sensitivity of NCFHEB binding to changes in endogenous ACh levels in up to 50 smoking and 50 nonsmoking subjects.**

**CLOSED Aim 5: To measure the sensitivity of NCFHEB binding to changes in endogenous ACh levels in up to 10 smoking and 10 nonsmoking subjects with schizophrenia.**

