### 3.7 Statistical analysis.

**3.7 a Power Analysis in Never Smokers:** Assuming Hardy-Weinberg equilibrium, the allele frequency predicts that 30 will be homozygous (CC); 25 will be heterozygous (CT) and 5 will be homozygous (TT) for the ANKK1 alleles, and 11 will be homozygous (AA) 29 will be heterozygous (AG) and 20 will be homozygous (GG) for the CHRNA5 alleles. In a one-way ANOVA analysis, sample sizes of 30, 25, and 5 are obtained from the three genotypes of ANKK1 whose means are to be compared. The total sample of 30 subjects achieves 0.96 power to detect differences among the means versus the alternative of equal means using an F test with a 0.05 significance level for thalamus. The size of the variation in the means is represented by their standard deviation which is 17.49. The common standard deviation within a group is assumed to be 32.30. The other powers are 0.95, 0.87, and 0.99 for ANKK1 for the brain regions of striatum, cerebellum and cortex, respectively. We have enough power to detect the effect with the proposed sample size. We aim to recruit at least 10 subjects that are homozygous for TT; if we do not achieve our goals for the rarer genotype by the end of year 3; we will screen subjects prior to imaging them in year 4.

**3.7.b Power Analysis in Smokers:** The group means of  $\alpha_2$ -nAChR availability for the heterozygotes of hCV16178933/rs2273504 or hCV15953820/rs2236196 are higher in smokers than non-smokers in the brain regions of striatum, cerebellum and mean cortex, but not thalamus. We can achieve 0.81 power to detect a difference of 11.7 in striatum between the null hypothesis that both group means are 97.5 and the alternative hypothesis that the mean of non-smoking group is 85.8 with estimated group standard deviations of 14.9 and 10.8 and with a significance level (alpha) of 0.05000 using a one-sided two-sample t-test for hCV16178933/rs2273504. The other powers are 0.97, 0.95 for hCV16178933/rs2273504 and for cerebellum and mean cortex, respectively. The differences do not present in the homozygote subjects. We can also achieve 0.98 to 0.99 for hCV15953820/rs2236196 in the brain regions of striatum, cerebellum and mean cortex.

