**Never Smokers:** In a one-way ANOVA analysis, sample sizes of 30, 25, and 5 are obtained from the three genotypes of ANKK1 whose means are to be compared. The total sample of 30 subjects achieves 0.96 power to detect differences among the means versus the alternative of equal means using an F test with a 0.05 significance level for thalamus. The size of the variation in the means

is represented by their standard deviation which is 17.49. The common standard deviation within a group is assumed to be 32.30. The other powers are 0.95, 0.87, and 0.99 for ANKK1 for the brain regions of striatum, cerebellum and cortex, respectively. We have enough power to detect the effect with the proposed sample size. We aim to recruit at least 10 subjects that are homozygous for TT; if we do not achieve our goals for the rarer genotype by the end of year 3; we will screen subjects prior to imaging them in year 4.

**Smokers:** The group means of  $b_2$ -nAChR availability for the heterozygotes of hCV16178933/rs2273504 or hCV15953820/rs2236196 are higher in smokers than non-smokers in the brain regions of striatum, cerebellum and mean cortex, but not thalamus. We can achieve 0.81 power to detect a difference of 11.7 in striatum between the null hypothesis that both group means are 97.5 and the alternative hypothesis that the mean of non-smoking group is 85.8 with estimated group standard deviations of 14.9 and 10.8 and with a significance level (alpha) of 0.05000 using a one-sided two-sample t-test for hCV16178933/rs2273504. The other powers are 0.97, 0.95 for hCV16178933/rs2273504 and for cerebellum and mean cortex, respectively. The differences do not present in the homozygote subjects. We can also achieve 0.98 to 0.99 for hCV15953820/rs2236196 in the brain regions of striatum, cerebellum and mean cortex.

Genotype quality control – genotyping error and missing genotype We will check the genotypes for the SNPs via the method of departures from Hardy-Weinberg equilibrium (HWE) developed by (157), and excluded genotyping errors as a likely cause of the disequilibrium. Genotyping errors and missing genotype/allele calls will be carefully examined. Those with genotyping errors will be assigned to be missing.

SECTION III: RESEARCH INVOLVING DRUGS, BIOLOGICS, RADIOTRACERS, PLACEBOS AND DEVICES

--

*If this section (or one of its parts, A or B) is not applicable, state N/A and delete the rest of the section.*

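### The 0.96 ANKK1 power is credited to 30 subjects but belongs to 60, and at the 10 never smokers of Aim 2 it is about 0.22

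*Combined protocol and SAP*

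**What the plan says.** The never-smoker power analysis in section 3.7a of the NCFHEB protocol describes a one-way ANOVA in which "sample sizes of 30, 25, and 5 are obtained from the three genotypes of ANKK1 whose means are to be compared". The next sentence reads "The total sample of 30 subjects achieves 0.96 power to detect differences among the means", for thalamus at the 0.05 level. The inputs given are 17.49 for the standard deviation of the means and 32.30 for the common within-group standard deviation. It then adds "The other powers are 0.95, 0.87, and 0.99 for ANKK1 for the brain regions of striatum, cerebellum and cortex, respectively" and concludes "We have enough power to detect the effect with the proposed sample size". The same section predicts that "11 will be homozygous (AA) 29 will be heterozygous (AG) and 20 will be homozygous (GG) for the CHRNA5 alleles". On the rare genotype it says "We aim to recruit at least 10 subjects that are homozygous for TT", with genotype screening before imaging in year 4 if that goal is not met. Section 12 (Statistical Considerations) repeats the ANOVA text, including the total of 30.

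The ANKK1 question belongs to Aim 2. The Statement of Purpose says that "10 never smokers and 10 smokers at one week of abstinence will be imaged using NCFHEB PET", and section 3.1 gives the same numbers: "genetically predisposed in 10 never smokers and 10 smokers at one week of abstinence with NCFHEB".

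Section 3.7b gives power 0.81 for a one-sided t-test in striatum (rs2273504 heterozygotes, smokers against nonsmokers, difference 11.7, standard deviations 14.9 and 10.8). It states no group sizes.

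**The concern.** Three sample sizes are in play for one power figure: 60 from the listed groups, 30 from the printed total, and 10 from the aim that poses the question. They cannot all support 0.96. Power decides how a null genotype result is read. At 0.96, a non-significant F test would be fair evidence against an effect of the assumed size. At about 0.22, non-significance is the likely outcome even if that effect is real. A reader who takes the printed power at face value would draw too strong a conclusion from 10 subjects.

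**Working it through.** **Inputs (section 3.7a).** Groups 30, 25, 5; standard deviation of means 17.49; within-group standard deviation 32.30; alpha 0.05; three groups. Aim 2 sample: 10 never smokers (Statement of Purpose; section 3.1).

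**Step 1, totals.** ANKK1: 30 + 25 + 5 = 60. CHRNA5: 11 + 29 + 20 = 60. The ANKK1 counts imply a T-allele frequency of (2 × 5 + 25)/120 = 0.292. Hardy-Weinberg proportions at 60 subjects then return 30.1, 24.8 and 5.1, so the listed counts were built on 60.

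**Step 2, power.** Effect size f = 17.49/32.30 = 0.5415, so f² = 0.2932. The F test has 2 and N − 3 degrees of freedom and noncentrality N × f². This treats 17.49 as weighted by group size, which is the reading that reproduces the plan's figure.

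| N | N × f² | Power | Basis for N |
|---|---|---|---|
| 60 | 17.59 | 0.964 | sum of listed groups; reproduces 0.96 |
| 30 | 8.80 | 0.709 | printed total |
| 20 | 5.86 | 0.496 | all Aim 2 subjects, smokers included |
| 10 | 2.93 | 0.219 | Aim 2 never smokers |

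On these inputs, 37 subjects are needed for power of at least 0.80.

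**Step 3, other readings.** If 17.49 is an unweighted standard deviation of the three means (divisor 3 or 2), power depends on the pattern of means. Scanning all patterns gives 0.21 to 0.84 at 30 subjects in the ratio 30:25:5, and 0.09 to 0.28 at 10 subjects split 5/4/1. Multiplying the noncentrality by 3/2 gives 0.88 at 30. A two-group test with the same f gives 0.33 at 10. None of these yields 0.96 at 30 or adequate power at 10.

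**Step 4, the TT goal.** The TT frequency is 0.292² = 0.085. Unselected, 10 never smokers give 10 × 0.085 = 0.85 expected TT subjects, and the chance of none is (1 − 0.085)^10, about 0.41. Sixty give 60 × 0.085 = 5.1. Ten TT subjects would occupy all 10 Aim 2 places and leave no comparison genotype.

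**Step 5, smoker contrast (section 3.7b).** The pooled standard deviation is √((14.9² + 10.8²)/2) = 13.01, so d = 11.7/13.01 = 0.899. One-sided power at alpha 0.05 is 0.800 for 16 against 16, 0.821 for 17 against 17, and 0.811 for 12 against 26. The sample size behind 0.81 therefore cannot be recovered. With Aim 2's 10 smokers and 10 never smokers, all assumed heterozygous, power is 0.61. That is the ceiling for those subjects.

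**Step 6, pooling.** Nonsmokers across Aim 1 (10), Aim 2 (10) and Aim 4 (up to 50) total at most 70. Thalamus power would be 0.984 at 70 and 0.923 at 50. Nonsmokers may join both Aims 1 and 4, so the distinct count may be below 70.

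**The case against.** The strongest reply is that the 30 is a slip, since the listed groups do give 0.96, and that the genotype analysis may draw on more than Aim 2. Willingness to donate blood for genetic studies is a general inclusion criterion, the sample is taken at intake, and Aims 1, 2 and 4 share one nonsmoker definition. If those nonsmokers are pooled, the adequacy sentence could be true. This stands as a possibility, and the fix allows for it. But no section declares pooling, and the Background ties the SNP work to Aims 2 and 3.

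A second reply is that 0.22 is not exactly the power of Aim 2's hypothesis. That hypothesis contrasts TT with heterozygotes, while 0.22 is for a three-genotype test in unselected proportions, and screening by genotype could change those proportions. This is fair: 0.22 illustrates the size of the gap and is not a precise value. The two-group figure of 0.33 is no more adequate.

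Third, the rs2273504 contrast comes from the Aim 3 hypothesis, which reuses the Aim 2 smokers, and for the smoker powers the defect is an unstated sample size, not a shown error. That also stands.

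Finally, Aims 2 and 3 are closed, so recruitment is not affected.

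**Conclusion.** The concern holds. The total of 30 is wrong in both section 3.7a and section 12; the quoted 0.96 is the power at 60. Sixty is six times the never smokers that Aim 2 images. At those 10 subjects power is about 0.22, with a range of 0.09 to 0.33 over the readings tried. The statement of sufficient power is unsupported for the only sample the documents tie to this question. The 0.22 assumes that 17.49 is weighted by group size and that genotypes fall in the listed proportions; the finding of inadequate power does not depend on either assumption. The conclusion would change only if pooling across aims were declared. The smoker powers cannot be checked without their group sizes. Because the aims are closed, the consequence is for interpretation, and the point should be corrected on that ground.

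**What to change.** In sections 3.7 and 12:

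1. Give 60, not 30, as the total behind the 0.96, and state the sample size behind the other ANKK1 powers.
2. Restate power at Aim 2's 10 never smokers (about 0.22 for thalamus, with its assumptions). If genotype analyses pool other aims, declare this and give the distinct number of subjects and its power.
3. Remove the adequacy sentence unless a declared sample supports it.
4. State the number per group behind each smoker power in 3.7b.
5. Reconcile the goal of at least 10 TT subjects, and the year-4 screening, with an aim that images 10 never smokers.

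The cost is a text change. No procedure or recruitment changes, but the stated power becomes less favourable unless pooling is declared.

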Our colleague, [name] has recently demonstrated that ANKK1 SNPs are strongly associated to nicotine dependence in European Americans and African Americans. Specifically the ANKK1 is in linkage disequilibrium with other variants that are associated with nicotine dependence as defined by DSM-IV criteria(123). This phenotype is particularly broad and thus may be related to one or more of smoking behaviors including, tolerance and withdrawal to name a few (123). The relationship between the ANKK1 gene and  $\beta_2$ -nAChR availability that we have observed in our pilot analyses is not entirely clear. However, it may be hypothesized that it may play a role in determining the phosphorylation state of nAChR subunits, which may modulate desensitization and recovery of the nAChR receptor in the presence and absence of nicotine (124). Tyrosine kinases regulate all nAChR but the functional consequences by the same kinase family are specific for each subtype and location [reviewed by (125)]. The  $\alpha_4$  subunit has been shown to be phosphorylated *in situ* by c AMP dependent protein kinase, (PKA) and protein kinase C (122). PKA mediated phosphorylation of the  $\alpha_4$  subunit enhances its affinity for the 14-3-3 chaperone protein resulting in increased expression of the  $\alpha_4\beta_2$  receptor(126) (127). The phosphorylation state of neuronal nAChRs appears to regulate their rate of recovery from desensitization and, receptors rely on balance between phosphorylation and dephosphorylation state to regain their agonist sensitivity(128). While it is known that the  $\alpha_4$  subunit exists in phosphorylated and dephosphorylated states, the relationship between these states and receptor function are not yet known (122). Additional work remains to elucidate the function of ANKK1 including more extensive expression profiling and characterization of the functional significance and localization at the protein levels(120) and its relationship to  $\beta_2$ -nAChR availability.

**In the present proposal we will explore the relationship of these and other SNPs (Aim 2 and 3) that have been linked to nicotine dependence with  $\beta_2$ -nAChR availability in never smokers and smokers to determine if these SNPs also convey genetic liability to  $\beta_2$ -nAChR availability in relation to the regulatory effects of nicotine as well as relapse rates.**

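### The NCFHEB protocol powers ten SNP-by-region tests at an unadjusted 0.05, with no primary test and no multiplicity rule

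*Combined protocol and SAP*

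**What the plan says.** The NCFHEB protocol's statistical text is section 3.7, repeated under item 12 (Statistical Considerations). Apart from genotype quality control, both contain only power statements.

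- **Never smokers (3.7a).** A one-way ANOVA compares three ANKK1 genotypes: "sample sizes of 30, 25, and 5 are obtained from the three genotypes of ANKK1 whose means are to be compared". The level is given once, for one region: "using an F test with a 0.05 significance level for thalamus". Three more regions follow without a restated level: "The other powers are 0.95, 0.87, and 0.99 for ANKK1 for the brain regions of striatum, cerebellum and cortex, respectively".
- **Smokers (3.7.b).** Among heterozygotes, smokers are compared with non-smokers. Striatum for rs2273504 has power 0.81, "with a significance level (alpha) of 0.05000 using a one-sided two-sample t-test for hCV16178933/rs2273504". Powers of 0.97 and 0.95 follow for cerebellum and mean cortex, and 0.98 to 0.99 for rs2236196 in the same three regions.
- **Further SNPs.** The Background section on genes associated with nicotine dependence says "we will explore the relationship of these and other SNPs (Aim 2 and 3"). Aim 3 also states a hypothesis for rs2273502, for which no power is given.

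Neither section names a primary SNP or region or gives a multiplicity rule. The PHNO protocol in the same file does have a rule (its section 3.7 and item 11): significance levels are adjusted by the number of related tests under each hypothesis. That protocol marks genetic testing as not applicable, so its rule does not reach these tests.

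**The concern.** Aims 2 and 3 ask whether receptor availability, and its change during abstinence, is genetically determined. Ten powered tests bear on them, and the plan does not say which of the ten would answer the question. If each is read at 0.05, a single nominally significant region for a single SNP can be presented as support, and the reader cannot tell how many looks stood behind it. The open SNP list, and the fifteen regions extracted under section 3.6, widen the choice further. The quoted powers also belong to the unadjusted level, so they overstate what an adjusted analysis could deliver.

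**Working it through.** **Inputs (section 3.7).** ANKK1: groups of 30, 25 and 5; SD of the means 17.49; within-group SD 32.30; level 0.05; four regions. rs2273504 and rs2236196: three regions each; one-sided 0.05; for rs2273504 in striatum, difference 97.5 − 85.8 = 11.7, SDs 14.9 and 10.8, power 0.81. Tests: 4 + 3 + 3 = 10. *Assumptions, not in the documents:* equal between-region correlation ρ from 0 to 1, and dependence between SNPs.

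**Step 1. Reproduce the plan's power.** f = 17.49/32.30 = 0.5415. Noncentrality λ = N·f². With N = 30 + 25 + 5 = 60, λ = 60 × 0.2932 = 17.59, and the noncentral F with 2 and 57 df gives 0.964, matching the stated 0.96. The total is written as 30 ("The total sample of 30 subjects achieves 0.96 power to detect differences among the means"); N = 30 gives 0.709, so 60 is used below.

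Smokers, striatum: noncentral t with unequal variances, one-sided 0.05, gives 0.798 at 16 per group and 0.820 at 17. The group size is not stated, so 16-17 per group is inferred from the 0.81.

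**Step 2. Chance of at least one false positive, independent tests.** 1 − 0.95^k:

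- k = 4 (ANKK1): 18.5%
- k = 6 (smoker tests): 26.5%
- k = 10: 40.1%

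**Step 3. Correlated regions.** Null simulation with F tests on groups of 30, 25 and 5 and one-sided t-tests at 16 per group, the three SNP families independent:

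| ρ | ANKK1, 4 tests | Smokers, 6 tests | All 10 |
|---|---|---|---|
| 0 | 18.5% | 26.5% | 40% |
| 0.5 | 16% | 22% | 35% |
| 0.8 | 12% | 18% | 27-28% |
| 0.9 | 10% | 15% | 23-24% |
| 1 | 5% | 10% | 14% |

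At ρ = 1 each SNP amounts to one test, and 1 − 0.95³ = 14.3%. If the two CHRNA4 SNPs selected exactly the same subjects, the ten-test figure would be 30% at ρ = 0, 17% at 0.9 and about 10% at 1 (1 − 0.95² = 9.75%). Partial overlap lies between.

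**Step 4. Power after adjustment.** Bonferroni over the four ANKK1 regions uses 0.05/4 = 0.0125. Thalamus uses f = 0.5415; for the other regions f is solved from the quoted power at N = 60 (0.521, 0.450, 0.613).

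| Region | Quoted, 0.05 | At 0.0125 |
|---|---|---|
| Thalamus | 0.96 | 0.89 |
| Striatum | 0.95 | 0.86 |
| Cerebellum | 0.87 | 0.71 |
| Cortex | 0.99 | 0.96 |

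For six smoker tests, 0.05/6 = 0.0083: striatum falls from 0.81 to 0.51-0.54 at 16-17 per group. Holm starts at these levels and relaxes after each rejection, so its per-test power is at least this high.

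**Step 5. Relation to the planned sample.** Aim 2 has 10 never smokers and 10 smokers. At N = 10 the thalamus inputs give power 0.22 even at 0.05.

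**The case against.** Four arguments on the other side carry weight.

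- *The plan states power, not decision rules.* This is true. The level is written out for only two of the ten tests, and the Background speaks of exploring the SNPs. A reader might infer that significance in any one region would be declared proof of genetic predisposition, but no section says so. What stands is the absence of any rule, not the presence of a bad one.
- *The range is assumed.* It is tempting to read 23-40% as the error rate of this plan. The lower end needs a between-region correlation of 0.9 and independent SNPs, and the documents give neither. Higher correlation or shared CHRNA4 heterozygotes lowers it. Nor is 40% a ceiling, since the SNP list is open.
- *Not every false positive is a false genotype effect.* Only the four ANKK1 tests compare genotypes. The other six could falsely show a smoking difference within heterozygotes. That still bears on Aim 3, which predicts higher availability in allele carriers than in matched never smokers, but not in homozygotes. The calculation also takes all ten nulls as true, although the Background reports receptor upregulation in abstinent smokers.
- *The regions are not interchangeable, and the aims are closed.* Section 3.6 treats thalamic change as the more interpretable and urges care in cortex. That is guidance on interpretation and names no primary region; 3.7.b does not power thalamus at all. Closure moves the remedy to analysis and reporting but leaves the gap.

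**Conclusion.** The point holds. The NCFHEB protocol has ten powered SNP-by-region tests, 0.05 as the only stated level, no primary test and no adjustment. Over the ten tests the familywise error exceeds 5% at every correlation examined: about 14-40% with SNPs independent, and down to about 10% if regions are perfectly correlated and the CHRNA4 SNPs select the same people. For ANKK1 alone it is about 5-19%, reaching the nominal level only when all four regions carry the same information. These figures rest on assumed correlations and on all nulls being true.

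A reader might also take 0.89 for thalamus as the study's power after adjustment. The documents do not support that: it needs the 60 subjects the genotype groups sum to, and Aim 2 has 10 never smokers and 10 smokers.

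**What to change.** Because Aims 2 and 3 are closed, naming a primary region now would be arbitrary. Instead:

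1. Declare the full SNP-by-region family in the analysis plan and in any report.
2. Apply the companion PHNO protocol's rule within each hypothesis, for example Holm over the four ANKK1 regions and Holm over the six smoker tests. This holds error at 5% per hypothesis; across the two families it could reach 1 − 0.95² = 9.75% if they are independent, and the report should say so.
3. Report adjusted p-values for all ten tests, whatever their result.
4. Label every other SNP and region exploratory.
5. Keep the smoker tests one-sided as stated, unless a reason for changing them is given.
6. Describe the six smoker tests as smoking differences within a genotype.

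The cost is wording and reanalysis; no new data are needed. Any power quoted must be restated at the adjusted level and will be lower, as shown above, and the N = 60 figures should not be attached to the Aim 2 sample.

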## 4. Genetic Testing N/A

### A. Describe

- i. the types of future research to be conducted using the materials, specifying if immortalization of cell lines, whole exome or genome sequencing, genome-wide association studies, or animal studies are planned

- One 10 mL tube of blood will be collected for DNA for testing of polymorphisms in genes of interest to nicotine dependence including ANKK1 and CHRNA4.

- ii. the plan for the collection of material or the conditions under which material will be received

-as above, a blood sample will be collected at intake to test polymorphisms of interest for nicotine dependence.

- iii. the types of information about the donor/individual contributors that will be entered into a database

- the genetic polymorphism results will be entered. The results of this testing will be confidential, will not be entered into the subject's medical record, and will not

iv. the methods to uphold confidentiality

- The results of genetic testing in locked file cabinets and by separating the personal identifying information of the subjects from the genetic information.

B. What are the conditions or procedures for sharing of materials and/or distributing for future research projects?

No sharing is planned.

C. Is widespread sharing of materials planned?

No.

D. When and under what conditions will materials be stripped of all identifiers?

It will not.

E. Can donor-subjects withdraw their materials at any time, and/or withdraw the identifiers that connect them to their materials? Yes.

i. How will requests to withdraw materials be handled (e.g., material no longer identified: that is, anonymized) or material destroyed)?

Subjects will be informed that their material has been anonymized.

F. Describe the provisions for protection of participant privacy

Risks associated with genetic testing will be minimized by keeping the results of genetic testing in locked file cabinets and by separating the personal identifying information of the subjects from the genetic information.

G. Describe the methods for the security of storage and sharing of materials

The results of genetic testing in locked file cabinets and by separating the personal identifying information of the subjects from the genetic information.

**5. Subject Population** Provide a detailed description of the targeted population of human subjects for this research project.

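### The stated target of at least 10 TT never smokers cannot be met together with the TT-versus-heterozygote comparison in an Aim 2 sample of 10 never smokers

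*Combined protocol and SAP*

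**What the plan says.** All references are to the NCFHEB protocol, the first of the two in the combined document.

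- **Target.** Section 3.7a (Power Analysis in Never Smokers), repeated in section 12 (Statistical Considerations): "We aim to recruit at least 10 subjects that are homozygous for TT". If the goal for the rarer genotype is missed by the end of year 3, "we will screen subjects prior to imaging them in year 4".
- **Enrolment.** Section II, Statement of Purpose, Aim 2: "10 never smokers and 10 smokers at one week of abstinence will be imaged using NCFHEB PET". Section 3.1 restates the aim as whether receptor availability "is genetically predisposed in 10 never smokers and 10 smokers at one week of abstinence with NCFHEB". Both places mark Aim 2 as closed.
- **Question and hypothesis.** Aim 2 asks whether genotype determines receptor "availability in adult never smokers". The hypothesis begins "Homozygotes (TT) will have higher" and sets TT against age- and sex-matched heterozygotes carrying the C allele.
- **Genotype frequencies.** Section 3.7a expects ANKK1 counts of 30 CC, 25 CT and 5 TT, and uses 30, 25 and 5 as the group sizes of a one-way ANOVA with a stated power of 0.96 in thalamus.

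**The concern.** The three figures do not fit together. Ten TT subjects would fill every never-smoker slot in Aim 2, although TT is expected in one never smoker in twelve. The hypothesis rests on the TT group. Someone reading the Aim 2 result beside the sample-size section would believe that the comparison had been planned with at least 10 TT subjects, when the stated enrolment would most likely yield none or one. With no TT subject the hypothesis cannot be tested at all.

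**Working it through.** **Inputs.** Genotype counts 30, 25, 5; standard deviation of the means 17.49; within-group standard deviation 32.30; alpha 0.05 (section 3.7a). Aim 2 never smokers: 10 (Statement of Purpose and section 3.1).

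**1. The plan's own power figure.** One-way ANOVA with three groups, noncentrality N × (17.49/32.30)², degrees of freedom 2 and N − 3.

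| N | Noncentrality | Power |
|---|---|---|
| 60 | 17.59 | 0.964 |
| 30 | 8.80 | 0.709 |
| 10 | 2.93 | 0.219 |

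The stated 0.96 reproduces at N = 60, the sum of the listed groups. It does not reproduce at the total of 30 printed in the same text. The row for 10 supposes that the genotype proportions are kept.

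**2. The genotype counts.** T-allele frequency = (25 + 2 × 5)/120 = 0.2917. Expected counts in 60 under Hardy-Weinberg equilibrium: 30.1, 24.8 and 5.1, in agreement with 30, 25 and 5. The TT proportion is 5/60 = 0.0833 from the rounded counts, or 0.2917² = 0.0851 unrounded.

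**3. TT subjects in 10 unselected never smokers.** Binomial with p = 1/12.

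- Expected number: 10/12 = 0.83
- P(none) = (11/12)^10 = 0.419
- P(exactly one) = 10 × (1/12) × (11/12)^9 = 0.381
- P(none or one) = 0.419 + 0.381 = 0.80 (0.79 with p = 0.0851)
- P(10) = (1/12)^10 = 1.6 × 10⁻¹¹

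**4. Other bases for the count, same p.**

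| Subjects | Expected TT | P(10 or more) |
|---|---|---|
| 20 (Aim 2 smokers added) | 1.67 | 1.4 × 10⁻⁶ |
| 60 (power section) | 5.0 | 0.026 |
| 120 | 10.0 | 0.55 |
| 149 | 12.4 | 0.80 |

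**5. With screening.** Suppose genotype screening supplied as many TT subjects as wanted. Slots left for heterozygotes = 10 − 10 = 0. This step needs no probability: whatever the selection, 10 TT and any comparator exceed 10 slots.

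**The case against.** **Year-4 screening.** The plan recognises that TT is rare and provides for screening before imaging. It does not say that all 10 never smokers would have been scanned by then. A reader might infer that the TT group was bound to be none or one; the documents do not support that, because the 0.80 holds only for unselected enrolment. Step 5 is unaffected.

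**Other aims.** The target sentence does not name Aim 2, and Aims 1, 2 and 4 share one nonsmoker definition. The plan states no pooling for the genotype analysis. As an assumption, 10 + 10 + 50 = 70 nonsmokers, an upper limit because controls may join more than one aim, would give 5.8 expected TT and a 0.064 chance of 10 or more. The group would then not be none or one, but the target would still probably be missed without screening.

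**Wasted scans.** A reader might infer that scans of other genotypes were uninformative. They were not: the planned ANOVA compares all three ANKK1 genotypes, Aim 2 also asks about CHRNA4, and Aim 3 needs never smokers matched on CHRNA4 genotype.

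**A single TT subject.** A reader might infer that one TT subject makes the comparison impossible. The plan assumes a common within-group standard deviation, so a pooled test exists, only a very imprecise one. With 1 TT and 4 CT (10 × 25/60 ≈ 4), the standard error of the difference is 32.30 × √(1/1 + 1/4) = 36.1.

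**Genotyping first.** Since "a blood sample will be collected at intake to test polymorphisms of interest for nicotine dependence", it is tempting to advise genotyping before every scan and giving slots to TT and CT subjects. Aim 2 is closed, nothing shows that slots remain, and such filling could empty the CC group of the ANOVA.

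**Overlap and weight.** The target appears to belong to text written for 60 never smokers, so it shares its origin with the error in the total sample size. Correcting 30 to 60 would not repair it, however, since 60 reaches 10 TT with probability 0.026. With the aim closed, what remains is how its result is read and whether the text is consistent; no open aim and no safety procedure is affected.

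**Conclusion.** The point stands as an internal contradiction in current text. At least 10 TT never smokers, 10 never smokers imaged, and a comparison with heterozygotes cannot all hold, with or without screening. For unselected enrolment on the plan's own frequencies, the TT group most probably numbers none or one (0.80), with a 0.42 chance that the hypothesis cannot be tested. These probabilities assume independent enrolment, TT at 5/60, and Aim 2 never smokers as the base; the last follows from the wording of both the aim and the power heading. The documents give no count of TT subjects actually imaged, so nothing here says what the closed aim in fact obtained.

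**What to change.** In sections 3.7a and 12, replace the target by the number of TT subjects Aim 2 can deliver: about 1 of 10 unselected never smokers or, now that the aim is closed, the number actually imaged. State beside it that the TT comparison is descriptive and not a powered test. Make the edit together with the correction of the sample size behind the 0.96 power, which requires 60 never smokers and not the 30 printed or the 10 imaged, so that both sections describe one sample. The cost is wording in two sections; no recruitment, scan or assay changes.
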